8.8 FIRST therapy clinical setting

Our therapy delivery and clinical governance partner and collaborator is Inspire; a mental health charity located in Northern Ireland (https://www.inspirewellbeing.org/) who delivered all therapies remotely in the feasibility trial. Inspire therapists are experienced in working remotely with cross-UK

and Republic of Ireland military veterans since online mental health assessment and therapy became mainstream therapeutic provision during the COVID-19 pandemic. In addition, participants in the feasibility trial reported Inspire therapists were knowledgeable, understanding and well-trained [25]. For an efficacy trial this third sector organisation offers a more *ideal setting* for the following reasons: a) the flow of participants through the trial is controllable because there are many fewer competing interests than within the NHS; b) Inspire, due to their Northern Ireland location, have considerable expertise in working with military veterans and other populations with occupationally-related PTSD; c) they have robust clinical governance procedures which are adaptable to being supplemented with FIRST therapy-specific clinical supervision.

8.9 Therapist recruitment and eligibility assessment

The trial requires twelve therapists to competently deliver FIRST as per the intervention delivery timeline. We recognise that twelve therapists introduces variability, of therapist effect for example [86] [87] but this is offset with the advantages of twelve providing greater external validity. Existing Inspire therapists who achieved competence while delivering therapy in the feasibility trial will be invited to apply to join the trial. Additionally, we will recruit 8-10 independently employed therapists who meet the following criteria:

- Hold full clinical registration with either the British Association for Counselling and Psychotherapy (BACP), the National Counselling and Psychotherapy Society, Accredited Professional Registrant (NCPS Acc.) the British Association of Behavioural and Cognitive Psychotherapy (BABCP), the United Kingdom Council of Psychotherapy (UKCP), the Irish Council for Psychotherapy (ICP), or equivalent.
- Candidates will be considered if they have completed their core training hours under a UKCP, ICP or BABCP approved training organisation and have completed a minimum of 250 client contact hours under clinical supervision.
- Practitioner Clinical/Counselling Psychologists must be registered with the Health Care Professions Council (HCPC).
- Trained in RTM, NLPt Trauma Therapy or Rewind technique.
- Current Professional Indemnity Insurance to £2.5 million.
- Clinical supervision with a BACP/UKCP/ICP/BABCP/HCPC accredited supervisor.
- Access NI, Garda vetting or mainland UK DBS equivalent clearance.
- Attended certified Safeguarding, Child Protection and Adults at Risk or in Need of Protection minimum level 2 training within the last three years.
- Work to the third sector delivery partners Risk Assessment, Management and Escalation Guidelines with adherence to regional Child Protection and Vulnerable Adults in need of protection policies, procedures and good practice guidance.
- Comply fully with the standards and key performance indicators set out in Inspire's associate counsellor agreement.
- Able to commit to the time required to complete the trial.

Once eligibility is determined they will be onboarded into Inspire as Associate Therapists. Inspire onboarding will comprise:

- Access NI or DBS clearance
- Induction into Inspire's operation and clinical policies and procedures
- Induction to Inspire's information management system
- Receipt of relevant documentary evidence of accreditation, certified child and adult safeguarding training, supervisor's report and professional indemnity insurance of £2.5 million.

8.10 Training and fidelity assessment of the delivery of FIRST protocol

Recruited therapists will participate in an additional seven hours, over a single day, of online training to orientate them to, and give opportunity to practice, the specific elements of the FIRST protocol which differ from previous reconsolidation protocols they have delivered clinically.

09.00	Introduction
09.10	Rationale for FIRST protocol
09.20	Simple PTSD
09.25	Complex PTSD
09.35	FIRST protocol steps
09.45	DES-11 assessment
10.00	Complex PTSD neutral activity process
10.30	BREAK
10.45	Complex PTSD video demonstration
12.30	BREAK
13.00	Protocol exercise in pairs x 2
15.00	BREAK
15.15	Variations to submodalities
15.45	Protocol principles
16.00	Research trial – [name]
17.00	CLOSE

Table 4. Programme – one day update for prior trained therapists

Following the one-day upskilling training, therapists will practice their skills on two work colleagues or friends or private clients. These sessions will be recorded and assessed for competency by an independent assessor. Following confirmation of FIRST delivery competence, therapists will participate in 14 hours of FIRST specific online clinical supervision delivered by the FIRST trainer in groups and individually via video call to ensure their continuing fidelity to the protocol.

8.10.1 Assessment of intervention fidelity

Because FIRST therapy takes place via a video call, and with participant informed consent (see below), each therapy session will be recorded using the online recording facilities within each video-conferencing interface. Once the session is completed the recording will be encrypted, password protected and saved to a secure KCL server. FIRST therapy is protocolised and is based on the principle that rapid dissociation from any hyperarousal state is key. It is very difficult to calibrate this on voice alone, particularly as the arousal response may occur before the client gets to the point of speaking. Therefore, to assess protocol fidelity, video-recordings of 10% (n=21) therapy sessions of the intervention received by participants will be randomly selected for fidelity checking by a FIRST therapist supervisor who provides independent expertise in reconsolidation protocols. Every three months client therapy sessions will be randomly selected by excel computer-generated random order number for fidelity assessment by this independent expert. Once assessment is complete for that *period*, therapy video recordings will be permanently deleted. The procedure will be repeated every three months in which FIRST is delivered. An adapted version of the Strengths Model Fidelity Scale [88] will be used to assess treatment fidelity. This measure aligns with FIRST's incorporation of strengths-based protocolised components therapy and a focus on keeping the client in a resourceful state. Therapists are required to adhere to the main constructs in strengths-based therapy while being sufficiently flexible to meet clients' needs.

8.10.2 Comparison intervention

Participants randomised to the waiting list control (WL) group can continue with any ongoing care or newly engage with usual care pathways available in NHS veterans' services and charities for non-PTSD mental health concerns. Participants will be offered FIRST therapy following the completion of data collection at 20 weeks post randomisation. They will be informed of the appointment date/time for FIRST therapy commencement at the point of randomisation. Safety data is collected at six and 12 weeks and our well-performing feasibility study safety protocol will ensure that any escalation of symptoms in waiting list participants will be detected and recorded as

an adverse event (Appendix 1).

9 Phase 1: Proof of concept study

9.1 Research question

Does FIRST have similar efficacy signals as RTM at 12 weeks with the same therapy dose?

9.2 Study design

This concords in size with the RTM arm of the feasibility trial and planned procedures for the main trial in phase 2 as described above. Outcome data collected at 12 weeks is appropriate because the mean PCL-5 score in the RTM group showed little difference between 12 weeks (35 (SD 17)) and 20 weeks (38 (SD 18)). The research procedures, except for randomisation and the mechanisms data collection procedures, are as for the main trial. Participants, setting, recruitment, informed consent and intervention details are presented in previous sections. Below are additional procedures only for the POC study.

9.3 Procedures

The 30 participants will be recruited in three months with completion of six-week safety data and 12-week follow up data on PTSD symptoms and depression symptoms. Participants will complete the mechanisms task battery proposed for the trial at baseline and 12 weeks (see Appendix 2).

9.4 Progression criteria

We will consider POC on the basis of the progression criteria detailed in table 5. These incorporate criteria and procedures to identify early signals that FIRST may/may not be working, two stop/go points are in the protocol (table 4) and observation of the PCL-5 MCID of 10 points (see analysis below). In the feasibility trial, 4 of 35 participants were deemed unsuitable by the therapist for the RTM protocol. Inability to stay in a neutral state and avoid emotional trauma flooding (becoming overwhelmed by their emotions) when sympathetic arousal was observed were the main reasons. Emotional trauma memory flooding is a contraindication for both RTM and FIRST protocols as ability to cognitively dissociate from the trauma experience is essential to the protocol delivery. Eligibility criteria will assess for this using the DES-11 [77] (see eligibility criteria and table 4).

9.5 Analysis

The statistical analysis plan (SAP) outlining all the analyses of the POC data will be developed during the trial set up period and before completion of the POC and will be signed off before any data analysis commences. In summary, the mean change from baseline to 12 weeks on PCL-5 scores of the FIRST POC cohort will be compared to the RTM arm data collected during the PETT feasibility study. We will estimate the mean and CI of the change in PCL-5 between baseline and 12 weeks, for the two cohorts. We will then compare them using both the mean change from baseline and the CIs of the mean change. We expect the CIs to be of similar width and to largely overlap if the treatment effect signal in the POC is similar to the treatment effect signal in the feasibility. We will compare the total number of therapy minutes of both RTM and FIRST therapy sessions completed to achieve the effect signal.

Table 5. POC study progression criteria using traffic light system (green represents 100%)
concordance with planned targets)

Progression criteria No (%) of (potential) participants		Rationale				
Eligible to proceed to	30 (100%)	In the feasibility trial 4/35 (11%) of participants				

receive FIRST therapy	≥27/30 (11%) <27/30 (>11%)	had contraindications to receiving RTM, identified post-randomisation at therapy commencement. We will evaluate our new general mental health eligibility assessment processes (pre- randomisation) to determine participants are FIRST-therapy ready.
Therapy toleration	≥25 (83%)	PTSD does not resolve itself without treatment so between and 15 and 30 participants (50% or
	15-24 (50- 82%)	over) tolerating therapy offers significant potential treatment gain.
	<15 (50%)	
Efficacy signal – proportion of participants	≥14 (45%)	Our feasibility trial found 48.5% of RTM participants met the 10-point MCID PCL4
reaching the 10-point MCID reduction at 12 weeks	9 -13 (30- 44%)	reduction at 20 weeks. PTSD does not resolve itself without treatment so with the potential of an efficacious brief therapy an equivalent efficacy
WEEKS	<9 (30%)	signal in at least 30 participants (50%) offers significant potential treatment gain.

10 Phase 2: Trial

The randomised controlled trial will run for 19 months with a five-month internal pilot. Data collection will continue up to the 20-week primary outcome timepoint for both arms of the study with 52-week maintenance of effect data collected for the Intervention arm only (see Appendix 2).

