8.2 Eligibility criteria

8.2.1 Inclusion criteria:

- UK based military veterans from the Royal Navy or Royal Marines, British Army, Royal Air Force;
- Aged >18 years;
- Currently living or working in the UK;
- Ability to read and speak English;
- PTSD diagnosis determined by DMS-5 using the Clinician Administered PTSD scale (CAPS-5)
- Experiencing symptoms causing clinically significant distress or impact on social, occupational or other areas of functioning;
- Self-reported history of exposure to one or more traumas;
- Willing and able to provide informed consent;
- Willingness to be randomised to treatment group;
- Willingness for the therapy sessions to be video recorded.
- Access to the Internet.

8.2.2 Exclusion criteria:

- Currently receiving psychological treatment for PTSD;
- Currently has a comorbid DSM-5 mental health or personality disorder sufficiently severe as to intrude upon the participant's ability to cooperate with treatment.
- Participants who have had a self-reported suicide attempt within the past month;
- Current dependence on alcohol as determined by an AUDIT cut off of ≥20 [76] or self-report of prescription or illegal substances dependence.
- An existing dissociative disorder as determine by scoring ≥43 on the Dissociative Experiences Scale [77]
- Self-reported medication changes in anti-psychotic and anti-depression medication in the previous four weeks.
- Any other documented reason in which the assessing assistant psychologists, in consultation with their clinical supervisor, determine that treatment for other mental health symptoms takes precedent over their PTSD at the time of assessment.

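### The proof-of-concept comparison of FIRST with RTM may favour FIRST, because the FIRST cohort is screened for therapy suitability and the RTM comparator, as described, is not

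*Protocol*

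**What the plan says.** The proof-of-concept (POC) question in protocol section 9.1 is: "Does FIRST have similar efficacy signals as RTM at 12 weeks with the same therapy dose". Section 9.5 answers it by setting the mean PCL-5 change from baseline to 12 weeks in about 30 FIRST participants beside the same quantity for RTM. In its words, "the mean change from baseline to 12 weeks on PCL-5 scores of the FIRST POC cohort will be compared to the RTM arm data" from the feasibility study. The two means and their confidence intervals are compared descriptively, with no margin and no covariate adjustment mentioned.

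Section 9.4 reports that "4 of 35 participants were deemed unsuitable by the therapist for the RTM protocol", mainly because of emotional flooding, and treats flooding as a contraindication for FIRST as well. Table 5 adds that these cases were "identified post-randomisation at therapy commencement".

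The FIRST cohort is screened for this problem before entry. Section 9.4 says the Dissociative Experiences Scale (DES) will be used to detect it. Section 8.2.2 excludes "An existing dissociative disorder as determine by scoring ≥43 on the Dissociative Experiences Scale". Table 5 says "We will evaluate our new general mental health eligibility assessment processes", with a top target of 30 out of 30 able to proceed and a middle band down to 27 out of 30. Table 3 in section 8.7 has a further stop point during priming for participants with a high DES score.

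The efficacy row of Table 5 asks for at least 14 of 30 responders at 12 weeks for green. Its rationale cites a 48.5% RTM responder share at 20 weeks.

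**The concern.** This is a historical comparison with no randomisation, so it depends on the two cohorts being alike. As described, they differ on a factor bearing directly on outcome: whether the person could receive the therapy at all. Any RTM participants who could not be treated, and who changed little, pull the RTM mean towards zero. The FIRST cohort is designed to contain few or none of them. The better the new screening works, the more of its benefit is credited to FIRST as a therapy.

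The protocol reports the 4 of 35 in the first row of Table 5, but does not connect it with the efficacy row of the same table or with the comparison in 9.5. That comparison is the answer to the POC research question, and the POC stage precedes a 215-participant trial.

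**Working it through.** **Inputs**
- Unsuitable in the RTM arm: 4 of 35 (9.4, Table 5). I read 35 as the size of that arm.
- RTM mean reduction at 20 weeks: 18 points (5.5).
- RTM PCL-5 mean at 12 weeks: 35, SD 17 (9.2).
- Baseline PCL-5, all feasibility participants: 57 (5.5). This gives an approximate 12-week RTM reduction of 57 − 35 = 22. It is approximate because 57 is not specific to RTM.
- RTM responder share at 20 weeks: 48.5% (Table 5).

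**Reproducing the plan's figures**
- 4/35 = 11.4%, stated as 11%.
- 16/33 = 48.48% rounds to 48.5%, whereas 17/35 = 48.57% rounds to 48.6%. The figure fits 16/33 better, but the denominator is not stated. If the arm had 35 people and 33 were counted, at most two of the four are missing from the 20-week figure, so two to four are in it. This is an inference, and the 12-week data could differ.

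**Mean change**

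Let N be the RTM participants analysed, k the unsuitable among them, M the arm's mean reduction and c the mean reduction in the unsuitable. Then

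mean reduction among suitable = (N·M − k·c) / (N − k).

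The documents do not give c. With c = 0 as an assumption:

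| N, k | M = 18 | M = 22 |
|---|---|---|
| 33, 2 | 18 × 33/31 = 19.2 (+1.2) | 22 × 33/31 = 23.4 (+1.4) |
| 33, 4 | 18 × 33/29 = 20.5 (+2.5) | 22 × 33/29 = 25.0 (+3.0) |
| 35, 4 | 18 × 35/31 = 20.3 (+2.3) | 22 × 35/31 = 24.8 (+2.8) |

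The shift is therefore about 1 to 3 points. With N = 35 and k = 4, moving c from −5 (worsening) to +10 (improvement) gives:
- smallest: 4 × (18 − 10)/31 = 1.0
- largest: 4 × (22 + 5)/31 = 3.5

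If k = 0, the shift is 0.

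**If unsuitable people also enter the FIRST cohort**

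Take equal efficacy in suitable people, 3 of 30 unsuitable in FIRST (the limit of the middle band) and c = 0. The FIRST mean is then 24.84 × 27/30 = 22.35 against 22, or 20.32 × 27/30 = 18.29 against 18. The bias falls to about 0.3 points.

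**Responder share, counting the unsuitable as non-responders**
- Two included: 16/31 = 51.6%, up 3.1 percentage points.
- Four included: 16/29 = 55.2%, up 6.7.
- On the alternative count: 17/31 = 54.8%, up 6.3 from 17/35 (48.6%).

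**Scale**

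The 95% confidence half-width for a mean change at n = 30 is t(0.975, 29) × SD/√30. That is 6.0 points for SD 16 and 7.5 for SD 20. A shift of 1 to 3 points is at most half of that.

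**The case against.** The strongest objection is that 9.5 is a summary. A separate POC statistical analysis plan is promised, and analysis sets normally belong there. That is fair for details such as which RTM participants are counted, and silence alone would be no finding. But 9.5 does fix the comparator and the method, a raw mean change against RTM arm data. An analysis plan that follows it as written inherits the mismatch.

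A second objection is that DES assessment is a declared stage of FIRST, so FIRST with its screening is compared with RTM as delivered. This does not remove the problem: people screened out never enter the FIRST mean, while their RTM counterparts may be in the RTM mean.

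Third, the mismatch may be small. The four were identified by therapist judgement of flooding, and nothing shows they would have scored 43 or more on the DES. Table 5 foresees up to 3 of 30 still unsuitable. The documents give neither 12-week data nor outcomes for the four. All of this stands, and it limits the claim to a possible bias of modest size.

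A reader might go further and infer that a worse FIRST would be passed to the main trial because of this mismatch. The chance of reaching 14 of 30 is 0.65 at a true 48.5% and 0.86 at 54.8%, which can look like support. It is not. Those probabilities describe a fixed cut-off at n = 30 and stay the same whichever RTM set is used. The cut-off is an absolute count, labelled 45%, already below the RTM share, and the mean-change comparison has no row in Table 5. The main trial then tests FIRST by randomisation against waiting list. Nor do the documents say that the whole arm as randomised is the analysed set.

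**Conclusion.** The concern holds in a limited form. The comparison in 9.5 may be biased in favour of FIRST, because a cohort screened for suitability is set against RTM data with no stated restriction, although 4 of 35 in that arm were found contraindicated after randomisation.

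The estimate of about 1 to 3 points on mean change, and about 3 to 7 percentage points on the 20-week responder share, rests on three assumptions: two to four of these people are in the RTM data, they had no mean change and did not respond, and none like them enter the FIRST cohort. If the four gave no data, or a similar share of the FIRST cohort proves unsuitable, the bias is near zero. The responder figures are at 20 weeks, and the 22-point reduction uses an all-participant baseline.

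A gap of this size could not be detected with these numbers: power is about 8 to 9% for 2.3 to 2.8 points with SD 17 and 30 per group. That limits what the comparison can show, but it does not excuse a bias whose likely direction is known in advance and which is cheap to reduce. The progression count in Table 5 is affected only indirectly, through the 48.5% in its rationale.

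**What to change.** In 9.5 and the POC analysis plan:

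1. Keep the all-enrolled comparison. State the RTM analysis set, and count suitability and stop-point failures the same way in both cohorts.
2. Show beside it a comparison restricted to therapy-suitable participants in both cohorts: RTM without the four, and FIRST without those who fail a suitability or stop-point check. Note that suitability was judged by the therapist in one cohort and by screening plus stop points in the other, so the match is closer but not exact.
3. In both comparisons, model 12-week PCL-5 on cohort and baseline PCL-5 in place of comparing raw mean changes. This handles differences in baseline severity; the restriction in step 2 handles suitability.
4. In the Table 5 rationale, quote the RTM responder share for both sets with their denominators. The threshold itself need not change for this reason.

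The cost is some wording and one extra analysis of feasibility data the team already holds. The downside is that the RTM benchmark may come out slightly higher.

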10.1 Baseline data collection

At baseline, consenting and eligible participants will complete primary, secondary and mechanisms outcomes, demographic and medical history questionnaires via Qualtrics online survey software. Socio-demographic and medical history variables collected are age, sex, ethnicity, occupational and co-habitation status, type and duration of military service and GP contact details. Related to their PTSD history we will collect data on PTSD symptoms, previous confirmed PTSD diagnoses, number of traumas and previous treatment attempts and current and previous three months' self-report pharmacotherapy and psychological therapies. Cognitive assessment data will be collected via PsychoPy software.

10.2 Data collection procedures (see Appendix 2)

Qualtrics survey software will be emailed to the participant for self-completion. They will also be offered support with completion from a researcher, if preferred.

PsychoPy experimental software will be used to build the cognitive task experiments with a web link to the experiment emailed to participants for self-completion. The PsychoPy team will provide support in building the experiment and will advise on experimental blocks, tasks and settings. The experiment will begin with information and instructions to the participants on how to complete the tasks. Each task should be completed without any interruptions. Participants will be given the option for a researcher to be online with them while completing the tasks. PsychoPy is compatible with all various servers and can be easily accessed via the study's URL.

These PROMS and mechanisms battery are extensive and present a considerable research burden. We achieved a 75% data completion rates [25] of across all outcomes at 20 weeks by developing and delivering empathic, compassionate and responsive relationships with participants. We will need to work harder to deliver this responsiveness to participants because of the added burden of the mechanisms battery which we will have evaluated in the POC study. Our PPI group have signposted us to ways to achieve this e.g ongoing positive social media messages from participants will be important for exemplifying our trustworthiness to the veteran community and for keeping people engaged. PPI support will continue to inform our engagement procedures.

